5.5 Additional analyses

5.6 Safety

Adverse events (severe lactic acidosis, cardiac ischaemia, acute kidney injury, and seizures) and any other possibly related adverse event, are recorded from randomisation until 30 days after randomisation or discharge from PICU, whichever is later

The percentage of patients experiencing one or more adverse event will be compared between groups using Fisher's exact test. Counts and percentages of adverse events, and serious adverse events, overall and by type, will be presented by allocated treatment group. Safety results will be reported for the ITT and PP populations.

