2.1 Trial design

Oxy-PICU is a pragmatic, open, multiple centre parallel group randomised controlled trial with integrated economic evaluation in infants and children accepted for unplanned admission to a participating PICU.

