2.8 Timing of outcome assessments

Following randomisation, observations are recorded hourly on the hour (+/-15 minutes) for 7 days (or until PICU discharge if earlier) and include receipt of invasive ventilation (yes/no) and, where children are on invasive ventilation, SpO2, mean airway pressure (MAP), and FiO2. For days 8 onwards (or until PICU discharge if earlier), the same observations are recorded twice daily at 09:00 and 21:00 (+/- 1 hour).

Receipt of any other type of organ support (yes/no) is recorded once daily until day 30 or PICU discharge.

Other outcomes are collected at discharge from critical care (date/time of liberation from ventilation, survival status at PICU discharge and discharge method, and functional status as measured using the Paediatric Cerebral Performance Category (PCPC) and Paediatric Overall

performance Category (POPC)), and at ultimate discharge from acute hospital (survival status at hospital and ultimate PICU discharge, locations of care after PICU discharge).

Specified adverse events and serious adverse events are collected from randomisation until 30 days after randomisation or discharge from PICU, whichever is later.

Long term survival is collected at 12 months, using either linkage to national survival data (NHS Digital) or by local research teams. Once 12 month survival status is known, PEDS-QL and CHU-9D quality of life questionnaire will be emailed or posted to consenting parents/legal guardians.

3 Statistical Principles

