3.1 Confidence intervals and p-values

The primary clinical outcome will be tested for superiority. Other secondary outcomes will be tested for superiority, where testing is specified, or summarised and reported using descriptive statistics. Statistical tests will be two-sided with significance set at P<0.05 unless otherwise specified. Effect estimates will be reported with 95% confidence intervals. There will be no adjustment for multiple testing. The results of subgroup analyses will be interpreted taking into account accepted criteria for credible subgroup effects²,³.

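### The only tested adverse-event percentage mixes four named events with others that count only if judged possibly related, in an open trial and with no test limited to the named events (minor)

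*SAP*

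**What the plan says.** SAP section 5.6 sets the scope of what is captured: "Adverse events (severe lactic acidosis, cardiac ischaemia, acute kidney injury, and seizures) and any other possibly related adverse event, are recorded". The window runs from randomisation to the later of day 30 and PICU discharge. The test follows: "The percentage of patients experiencing one or more adverse event will be compared between groups using Fisher's exact test". Nothing narrows it to the named types. The rest is descriptive: "Counts and percentages of adverse events, and serious adverse events, overall and by type, will be presented by allocated treatment group". Safety results are to be given for both the ITT and the per-protocol populations.

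Three other sections bear on this.

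- Section 2.1 gives the design: "Oxy-PICU is a pragmatic, open, multiple centre parallel group randomised controlled trial".
- Section 2.8 describes collection without any relatedness condition and names no assessor: "Specified adverse events and serious adverse events are collected from randomisation until 30 days after randomisation or discharge from PICU, whichever is later".
- Section 3.1 sets the threshold, "Statistical tests will be two-sided with significance set at P<0.05 unless otherwise specified", and adds "There will be no adjustment for multiple testing".

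**The concern.** The tested numerator has two parts with different entry rules. A child with severe lactic acidosis, cardiac ischaemia, acute kidney injury or a seizure counts whatever the cause. A child with any other event counts only if that event is thought possibly related. For this second part, an opinion about the effect of treatment helps decide who counts in the test of that effect.

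In an open trial with visibly different saturation targets, the same event could be called possibly related more often in one arm. Neither randomisation nor analysis by allocated group removes such a difference. This is the only adverse-event comparison for which the SAP specifies a test, so its p-value is the one likely to be cited as the safety result. A gap in labelling could push that p-value below 0.05 when event rates are equal. It could also offset a real difference in the named events.

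**Working it through.** **Plan's own figure.** There is none to reproduce: the SAP states no adverse-event rate, no frequency of other events and no power for the safety test. Everything below except the sample size, the test and the 5% level is an assumption.

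**Inputs from the SAP.** Section 2.3 gives 2040 children with a 10% allowance for withdrawal or refusal of consent, and section 2.2 gives 1:1 allocation. So 2040 × 0.90 = 1836 analysed, or 918 per arm. The test is Fisher's exact (5.6), two-sided at 0.05 (3.1).

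**Model.** Let q be the percentage with a named event, the same in both arms, and x the percentage with an other event that was labelled possibly related. Taking the two as independent within a child, the tested percentage in an arm is

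p = 1 − (1 − q)(1 − x).

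The rejection probability is the sum, over all pairs of counts (i, j), of the two binomial probabilities (918 children; p₁ and p₂) for those pairs where Fisher's p is below 0.05. True event rates are equal; only the labelling differs.

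**Worked case, q = 5%.**

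- x = 1%: p = 1 − 0.95 × 0.99 = 5.95%, about 55 of 918.
- x = 3%: p = 1 − 0.95 × 0.97 = 7.85%, about 72 of 918.

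A gap of 1% v 3% arises, for example, if 4% of children in each arm have an other event and 25% v 75% of these are labelled related.

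**Rejection probability with equal true rates, 918 per arm**

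| Named-event rate | 1% v 1% labelled | 1% v 2% | 1% v 3% | 1% v 4% |
|---|---|---|---|---|
| 3% | 3.8% | 14% | 44% | 76% |
| 5% | 4.0% | 11% | 33% | 62% |
| 10% | 4.2% | 8% | 20% | 40% |

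At q = 5%, a gap of 1% v 1.5% gives about 6%. So does the case where 2% have an other event and 25% v 50% of these are labelled related (0.5% v 1%).

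**Smallest excess that reaches p < 0.05, 918 per arm**

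| Lower arm | Higher arm | Excess |
|---|---|---|
| 9 (1%) | 21 | 12 |
| 18 (2%) | 33 | 15 |
| 46 (5%) | 68 | 22 |
| 92 (10%) | 120 | 28 |

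**Masking.** Suppose named events truly differ, 3% v 5%, and labelling runs the other way, 3% v 1%. The tested percentages are 1 − 0.97 × 0.97 = 5.91% and 1 − 0.95 × 0.99 = 5.95%. The two-point difference disappears from the pooled figure.

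**What a named-only test gives up.** With q = 3% and x = 4%, p = 1 − 0.97 × 0.96 = 6.88%. Testing named events alone leaves 3%, so 3.88/6.88 = 56% of the affected children drop out of the test. With q = 5% and x = 1% the loss is 0.95/5.95 = 16%.

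**The case against.** **Who judges relatedness.** A reader might infer that relatedness is judged by staff who know the allocation. The SAP does not say so. It names no assessor, and an open design does not rule out central or masked review, which could be set out in the protocol (not shown here). This objection stands, and the point does not depend on the inference: section 5.6 specifies no masked attribution, and the proposed change is sound whether or not such a review exists.

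**Whether pooling hides the named events.** A reader might also infer this. It does not, because counts and percentages are to be presented by type and by arm. A difference driven by the other events would be visible in the same report. What remains is that the only specified test uses the pooled figure.

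**Size.** All rates are assumed, and a labelling gap of half a point barely moves the rejection rate. A significant result from labelling alone becomes likely only if the gap is large and other events are common relative to the named ones. This stands as a limit on the point.

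**The broader category has a purpose.** Unanticipated harm would show up among the other events, so dropping them from all testing would be a trade-off rather than a correction. A named-event test is not free of open-label influence either, since detecting some named events may depend on how closely children are watched. Both remarks are fair. They argue for keeping the pooled percentage as a supporting result, not for leaving it as the only test.

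**Consequence.** Mortality at PICU discharge and at 30 days is tested separately (section 5.2.2) and needs no relatedness judgement. The adverse-event test is neither the primary outcome nor part of the stopping rule in section 2.6.

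**Conclusion.** The point holds as a minor one. On its plain text, section 5.6 pools events counted whatever their cause with events counted only if judged possibly related, and tests the mixture in an open trial. It specifies neither masked attribution nor a test limited to the named events. A large labelling gap could therefore create or conceal a significant difference.

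At an assumed 5% named-event rate the false rejection rate moves from about 4% to 11%, 33% and 62% as the labelled percentage in one arm rises from 1% to 2%, 3% and 4% against 1% in the other. The effect is weaker at a 10% named-event rate and stronger at 3%. These figures rest on 918 per arm, equal true rates, independence of the two kinds of event, and labelling rates that no document supplies. They show what could happen, not that biased attribution is expected. The primary analysis and the mortality comparisons are unaffected.

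**What to change.** In section 5.6:

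1. Make the main tested comparison the percentage of children with at least one of the four named events, counted regardless of relatedness.
2. Keep the pooled percentage, and the other possibly related events by arm, as supporting results.
3. Add a note that inclusion of the other events depends on a relatedness judgement in an open trial. If the protocol provides for masked attribution, cite it here.

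The cost is a few sentences of SAP text, with no new data and no change to collection. The drawbacks are that the main test has fewer events, possibly far fewer if other events are common (16% to 56% fewer affected children in the two cases worked above), and that unanticipated harms are assessed only in the supporting results.

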2.3 Sample size

The primary clinical outcome will be analysed using rank-based methods, with death at 30 days ranked as the worst outcome. To achieve 90% power, using simulations based on data from the Oxy-PICU pilot RCT, to detect a clinically meaningful reduction in the mean duration of organ support of 12 hours from 120 to 108 hours and assuming no impact on 7.5% mortality requires a total sample size of 2040 patients (allowing for withdrawal/refusal of deferred consent of 10%).

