5.2.2 Secondary outcomes

Mortality at discharge from critical care and at 30 days will be compared between groups using Fisher's exact test. If the number of events allows, logistic regression will be used to compare mortality between groups adjusted for baseline variables.

Mortality at 90 days and at 12 months will be estimated by arm, using Kaplan-Meier methods with patients censored at last available follow-up. If the number of events allows, Cox regression will be used to compare mortality between groups adjusted for baseline variables.

Time to liberation from ventilation will be reported as median time (with 95% confidence interval) by arm, calculated using Kaplan-Meier methods. Unadjusted and adjusted hazard ratios will be calculated using Cox regression. Patients who die on ventilation will be censored at date & time of death.

Duration of organ support to day 30 (calculated as for the primary clinical endpoint) will be compared between groups using a Wilcoxon rank-sum test, in patients stratified by survival status. Duration of organ support by type of support (respiratory invasive; respiratory non-invasive; cardiovascular; renal; other) will be reported by group using medians and interquartile ranges, and counts and percentages of patients ever receiving, but not formally tested for differences between groups. Length of PICU and acute hospital stay will be compared between groups using a Wilcoxon rank-sum test, and reported by group using medians and interquartile ranges, in patients stratified by survival status.

Functional status at PICU discharge will be reported as counts and percentages in each of five possible categories.

All adjusted analysis will include the baseline variables previously listed in section 5.2.1.

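### The tested adverse event window runs past day 30 only for children still in PICU, so it depends on a post-randomisation outcome; the expected bias is small and a day-30 cut removes it

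*SAP*

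**What the plan says.** SAP 2.8 sets the collection window: "Specified adverse events and serious adverse events are collected from randomisation until 30 days after randomisation or discharge from PICU, whichever is later". SAP 5.6 repeats it for the listed events and any other possibly related event, which "are recorded from randomisation until 30 days after randomisation or discharge from PICU, whichever is later". The two sections agree.

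For analysis, 5.6 states: "The percentage of patients experiencing one or more adverse event will be compared between groups using Fisher's exact test". It also promises counts and percentages by type and arm, in the ITT and per-protocol populations. It gives no day-30 cut for the tested percentage, no rate per time observed and no time-to-event analysis.

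Two other sections bear on this. In 5.2.2, PICU stay is itself an outcome: "Length of PICU and acute hospital stay will be compared between groups using a Wilcoxon rank-sum test". In 2.7, the database is locked and the main analysis run when every randomised child has reached the 30-day timepoint. The only later update planned is for long-term outcomes.

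**The concern.** A crude percentage with any event compares risk fairly only if the planned observation window does not depend on treatment. Here part of it can. Up to day 30 the window is common to both arms. After day 30 it continues only for children still in PICU, and how many remain, and for how long, is known only after randomisation and may differ by arm. Any such difference feeds into the tested percentage even if the daily event risk is identical, and Fisher's test cannot separate the two.

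Timing adds a second problem. A child recruited early who stays past day 30 contributes the whole window to the main analysis. A child recruited near the end may still be in PICU at database lock, with the window unfinished. The tested quantity then also varies with recruitment date.

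The stated aim (1.2) is to set the risks of the interventions against their benefits, so the safety comparison should be as clean as the primary clinical outcome, which already uses a fixed 30-day horizon (5.1.1).

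**Working it through.** **The plan's own figures.** The SAP states no event rate, no distribution of PICU stay and no power for the safety comparison, so there is no figure to reproduce. From 2.3 come the sample size, 2040 × 0.9 = 1836 analysed, or 918 per arm, and the target "to detect a clinically meaningful reduction in the mean duration of organ support of 12 hours from 120 to 108 hours", "assuming no impact on 7.5% mortality". The 2040 came from simulations on pilot data and no SD is given. Solving a two-mean formula backwards gives 12 × √(918/2) / (1.96 + 1.2816) ≈ 79 hours, a coefficient of variation (CV) of 79/120 ≈ 0.66. That serves only as the lower end of the spread below.

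**Step 1: who is watched longer.** Planned window = max(720 h, PICU stay), since 30 × 24 = 720. Differences in stay below 720 h leave it unchanged.

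**Step 2: share past day 30.** Assumptions: lognormal stay; the design means for organ support used as a stand-in for PICU stay; then stays twice as long; deaths ignored. With σ² = ln(1 + CV²) and μ = ln(mean) − σ²/2:

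- P(stay > 720) = 1 − Φ((ln 720 − μ)/σ)
- mean excess = mean × Φ((μ + σ² − ln 720)/σ) − 720 × P(stay > 720)

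| CV | Past day 30, 120 v 108 h | Window difference | Past day 30, 240 v 216 h | Window difference |
|---|---|---|---|---|
| 0.66 | 0.05% v 0.03% | 0.03 h | 1.67% v 1.06% | 1.3 h |
| 1 | 0.51% v 0.35% | 0.4 h | 4.13% v 3.13% | 4.0 h |
| 1.5 | 1.41% v 1.10% | 1.5 h | 6.00% v 4.93% | 7.3 h |
| 2 | 2.03% v 1.66% | 2.5 h | 6.68% v 5.67% | 9.4 h |
| 3 | 2.62% v 2.23% | 3.9 h | 6.91% v 6.03% | 12.0 h |

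The mean windows differ by at most about 0.5% on the design means and 1.5% with stays doubled.

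**Step 3: spurious difference.** Difference = (gap in share past day 30) × P(first event after day 30). Assume the second factor is 0.10 to 0.30.

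- Design means, largest gap 2.62 − 2.23 = 0.39 points: 0.04 to 0.12 points. Per 918 children, about 0.4 to 1.1.
- Stays doubled, largest gap 6.00 − 4.93 = 1.07 points: 0.11 to 0.32 points. Per 918 children, about 1 to 3.

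**Step 4: effect on the test.** Let p be the share with an event by day 30 (5% to 20%), h = −ln(1 − p)/30 the daily rate, q the share past day 30, extra stay exponential with mean 20 days, and m the multiple of the daily rate after day 30 (1 or 3). Then

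P(any event) = p + (1 − p) × q × [1 − 1/(1 + 20mh)].

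Type I error is for a two-sided 5% test by normal approximation, 918 per arm.

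| q by arm | Spurious difference (points) | Type I error |
|---|---|---|
| 2% v 1.5% | 0.02 to 0.12 | 0.050 to 0.051 |
| 5% v 4% | 0.03 to 0.25 | 0.050 to 0.052 |
| 5% v 3% | 0.06 to 0.49 | 0.050 to 0.058 |
| 10% v 8% | 0.06 to 0.49 | 0.050 to 0.057 |
| 10% v 5% | 0.16 to 1.23 | 0.053 to 0.098 |

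Worked extreme: p = 0.20, h = 0.00744, m = 3, so 20mh = 0.446 and the bracket is 0.309. The difference is 0.80 × 0.05 × 0.309 = 1.23 points.

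**Step 5: with a day-30 cut.** Both arms have the same planned 720 h and the difference due to the window is zero.

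**The case against.** The other side has a good case. Sections 2.8 and 5.6 agree with each other, and collecting events for as long as a child is in PICU is coherent. The taking of the later date gives all children a common 30-day minimum, so for nearly all of them a shorter stay changes nothing. The Fisher test is also not the only safety evidence, since events are tabulated by type and arm. All of this stands and is why the point is minor.

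A reader might infer that whichever arm has the longer PICU stay is watched longer, so that shortening stay buys an apparent safety advantage. The SAP does not support that: a fall in stay from 8 to 6 days leaves the window at 30 days. Only differences in stays beyond day 30 count.

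A reader might also reach a larger figure, for example 8% v 5% past day 30 with a 30% chance of a late first event: 0.03 × 0.30 = 0.9 points, about 8 children per 918. That needs a relative fall of 37.5% in the long-stay share, against a 10% fall in the design mean (12/120). Nothing in the SAP supports it.

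Finally, deaths before day 30 (7.5% assumed) end observation early and outnumber the stays past day 30 in every row of the step 2 table. Refusal of records access also stops collection (4.4). A day-30 cut cures neither. It does remove the part of the window that the plan itself ties to PICU stay, and the design assumes mortality is equal between arms.

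What the objection does not answer is that the tested window depends on an outcome and may be unfinished for late recruits at the main analysis.

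**Conclusion.** The point holds as a minor one. The tested window in 5.6 is common to day 30 and then extends only for children still in PICU. Under 2.7 that extension may be incomplete for late recruits; how often depends on the interval between the last child's day 30 and database lock, which the SAP does not give.

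On design-linked assumptions the spurious difference is about 0.1 percentage points, roughly one child per arm, with type I error close to 0.05. A material distortion (1.2 points, error about 0.098) needs an extreme split such as 10% v 5% past day 30, together with a threefold late event rate and a 20% event share by day 30. These sizes rest on an assumed lognormal stay, organ support means standing in for PICU stay, and assumed event rates. The SAP supplies none of these, so the sizes are a guide and not an estimate.

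**What to change.** In 5.6, apply Fisher's exact test to the percentage of children with at least one event with onset from randomisation to day 30 inclusive, stating how days are counted (5.1.1 takes the day of randomisation as day 1). Report events with later onset separately by arm, without a test, noting any child still in PICU at database lock.

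The cost is one or two sentences in the SAP and a filter on onset date. Collection under 2.8 is unchanged, and the tested window is then complete when 2.7 triggers the main analysis. The downside is that a few late events leave the tested percentage, though they stay reported. Deaths before day 30, and refusal or withdrawal of data access among any children kept in the safety analysis, will still shorten observation, and the report should say so.

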3.3 Analysis Population

Following the intention to treat (ITT) principle, all randomised patients will be included in the analysis of the primary clinical endpoint, excluding only those where consent to access medical records was withheld or unobtainable (or were lost to follow-up before PICU discharge for any other reasons) before 30 days post randomisation.

A sensitivity analysis will be conducted in the per-protocol (PP) population, consisting of all randomised patients excluding those who were found to have breached the eligibility criteria following randomisation, and those where a clinical decision not to follow the trial treatment was recorded immediately post randomisation.

4 Trial population

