4.4 Consent

The parent/legal guardian of trial participants will be asked to consent to the study as soon appropriate and practical after randomisation (usually within 24-48 hrs of randomisation but the timing will vary according to the child's clinical situation). They may consent to any one or more of the following aspects: Trial continuation (i.e. treatment); access to medical records for ongoing data collection; completion of the parental stress questionnaire (at/around the time of consent); to receive a follow-up questionnaire at 6 months post-randomisation; sharing of anonymised data to support future research; to be contacted regarding future research participation. When consent is refused for access to medical records (regardless of whether or not consent has been given for trial continuation), all trial data collection should cease and no data linkage to PICANET or NHSDigital should be performed. Data collected by site staff directly to the trial CRF up to the point of consent refusal will be retained and used for analysis, but no events after this point will be recorded or reported on. If any data has already been obtained via linkage from PICANET or NHSDigital, this data will be deleted.

Where consent has been refused for trial continuation, but granted for access to medical records, data collection and linkage may continue and the patient may be included in the analysis as appropriate for each endpoint.

If consent is refused for access to medical records and/or trial continuation, the parental stress questionnaire may still be completed and reported on if this has been consented to.

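### The ITT safety table leaves out adverse events recorded before consent refusal, and the two safety sets are not nested as written

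*SAP*

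**What the plan says.** SAP section 5.6 compares the percentage of children with at least one adverse event by Fisher's exact test and tabulates adverse and serious adverse events by arm. It ends: "Safety results will be reported for the ITT and PP populations". No separate safety set is defined.

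The only ITT definition is in section 3.3. It says that "all randomised patients will be included in the analysis of the primary clinical endpoint". Its exception is worded "excluding only those where consent to access medical records was withheld or unobtainable", and it adds children whose follow-up ended while they were still in PICU; either must fall before day 30. The per-protocol set is a different subtraction: "consisting of all randomised patients excluding those who were found to have breached the eligibility criteria following randomisation", and also without children for whom a clinical decision against the trial treatment was recorded straight after randomisation. Refused consent is not on that list.

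Section 4.4 places the consent discussion after randomisation, "usually within 24-48 hrs of randomisation but the timing will vary according to the child's clinical situation". On refusal of record access it says: "Data collected by site staff directly to the trial CRF up to the point of consent refusal will be retained and used for analysis". Later events are not recorded, and data already obtained by linkage are deleted. Section 4.5 likewise keeps data collected before a withdrawal.

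Section 5.4 brings children without data consent back in extreme-case sensitivity analyses of the primary clinical endpoint. It has no counterpart for safety.

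**The concern.** The section 3.3 exclusion has a reason that belongs to the primary outcome: a 30-day score cannot be completed for a child whose records are closed. An adverse event already on the CRF does not need day-30 follow-up. Applying the same set to safety removes events that were observed under the allocated target, are held in the database, and are described in section 4.4 as usable.

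The trial is open, so a parent's decision on consent could be influenced by an early event. If that happened more in one arm, the ITT comparison would understate the harm in that arm. The per-protocol table is not a clean backstop: it removes other children, and the SAP does not say whether it sits inside ITT.

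**Working it through.** **Step 1. Who is in which set, on the literal text.**

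| Child | ITT (3.3) | Per-protocol (3.3) | CRF data up to that point (4.4, 4.5) |
|---|---|---|---|
| Record consent refused or unobtainable before day 30 | out | in (no consent exclusion listed) | kept; for refusal, usable for analysis |
| Lost before PICU discharge, before day 30 | out | in (not listed) | no rule for removal |
| Treatment continuation refused, record access allowed | in | in | kept, collection may continue |
| Eligibility breach found after randomisation | in | out | kept |

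Rows 1 and 4 show that neither set contains the other.

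**Step 2. The plan's own allowance.** Section 2.3 gives 2040 children, "allowing for withdrawal/refusal of deferred consent of 10" per cent. The total of 2040 comes from simulation on pilot data that are not shown, so it cannot be reproduced. The inflation step is consistent: 1836 / (1 − 0.10) = 2040. The allowance is 2040 × 0.10 = 204 children, or about 102 per arm.

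**Step 3. Children with an omitted event.** The SAP gives no event rates. If between 1% and 10% of those 204 had an event before refusal (an assumption), the number omitted is 204 × 0.01 ≈ 2 to 204 × 0.10 ≈ 20.

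**Step 4. When does the omission bias the comparison?** Illustrative assumptions, none from the SAP: 1020 per arm; events in p = 7% and 4% of children; a share f of events falls before the consent decision; refusal is r after such an early event in the higher-event arm, and 10% for all other children. Events after refusal are not recorded.

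- Restricted to the ITT set: [p·f·(1 − r) + p·(1 − f)·0.9] / [p·f·(1 − r) + (1 − p·f)·0.9]. In the lower-event arm this is 4.0%.
- All randomised: p·f + p·(1 − f)·0.9.

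Example, f = 1 and r = 0.20: 0.056 / (0.056 + 0.837) = 6.27%, a difference of 2.3 points.

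Example, f = 0.25 and r = 0.10: all randomised gives 0.0175 + 0.0525 × 0.9 = 6.475% and 0.01 + 0.03 × 0.9 = 3.70%, a difference of 2.8 points. The restricted set gives 3.0.

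| f | r, higher-event arm | Difference, ITT set (points) | Difference, all randomised (points) | Fisher power, ITT set vs all randomised (simulated, approximate) |
|---|---|---|---|---|
| 1 | 10% | 3.0 | 3.0 | 79% vs 82% |
| 1 | 20% | 2.3 | 3.0 | 58% vs 82% |
| 1 | 25% | 1.9 | 3.0 | 45% vs 82% |
| 1 | 30% | 1.5 | 3.0 | 31% vs 82% |
| 0.5 | 20% | 2.6 | 2.9 | 70% vs 81% |
| 0.25 | 10% | 3.0 | 2.8 | – |
| 0.25 | 20% | 2.8 | 2.8 | 74% vs 78% |
| 0.25 | 30% | 2.6 | 2.8 | 71% vs 80% |

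Refusal unrelated to events does almost no harm. The loss grows with both the share of early events and the selectivity of refusal.

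**The case against.** The SAP can be read more kindly. The section 3.3 exclusion is worded for the primary endpoint alone, and section 4.4 says data recorded before refusal are used. Together these could mean that every randomised child counts for safety until refusal. This stands in part: the SAP contains no sentence ordering these events to be left out. But section 5.6 calls on the ITT population, only one is defined, and a programmer following it would leave them out. A formal test between arms should not have two possible denominators.

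A reader might infer that the omitted events appear in no adverse-event table at all. The text does not support that: the per-protocol definition does not exclude refusers, so read literally their events would appear there.

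A reader might also take the fall to 31% power as the expected cost. That figure needs every event to precede the consent decision and refusal to triple after an event in one arm only. Nothing in the SAP supports either condition. Consent is usually sought within one to two days, while events are collected to day 30 or beyond.

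Finally, counting all randomised children has its own cost. Refusers enter the denominator in full with only short observation, which pulls the difference from 3.0 to 2.8 points when a quarter of events are early and refusal is equal. Reporting child-days shows this but does not correct the Fisher test. This stands, and it is why the added analysis should sit beside the ITT result and not displace it.

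**Conclusion.** The point holds as a mismatch between sections 3.3, 4.4 and 5.6. Followed as written, the ITT safety table and its Fisher test omit adverse events that the SAP retains for analysis, for a reason that applies only to the day-30 endpoint. The ITT and per-protocol sets are also not nested on the literal text.

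The 204 children are a ceiling and not a forecast: the 10% covers withdrawal as well as refusal, and children whose parents decline only treatment continuation stay in. The number of omitted events cannot be derived from the SAP; about 2 to 20 children rests on assumed rates of 1% to 10%. Bias in the comparison is material only if refusal is related to an early event. The primary clinical result is not affected, and events after refusal cannot be recovered under any choice of set.

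**What to change.** In section 5.6, add a safety analysis of all randomised children by allocated group. Count every adverse event and serious adverse event entered on the CRF up to refusal, withdrawal or the end of the reporting window, and leave out linked data that section 4.4 requires to be deleted. Report child-days of observation per arm and present this analysis alongside the ITT result. In section 3.3, state whether the per-protocol set is a subset of ITT.

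The cost is a few lines of SAP text and one further table from data already held. The downside is the slight dilution from refusers' short observation, which the child-days make visible. No clinical procedure changes.
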